6.2.6 Other Immune-Mediated Adverse Reactions

Other clinically significant immune-mediated adverse reactions can occur. Immune-mediated adverse reactions may occur after discontinuation of nivolumab therapy. For any suspected immune-mediated adverse reactions, exclude other causes. Based on the severity of the adverse reaction, withhold nivolumab, administer high-dose corticosteroids, and if appropriate, initiate hormone-replacement therapy. Upon improvement to Grade 1 or less, initiate corticosteroid taper and continue to taper over at least 1 month. Consider restarting nivolumab after completion of corticosteroid taper based on the severity of the event

6.2.7 Immune Mediated Cardiac Toxicity

Cardiac *	Management/Next Dose for Nivolumab
≤ Grade 1	Hold dose pending evaluation and observation.** Evaluate for signs and symptoms of CHF, ischemia, arrhythmia or myositis. Obtain history EKG, CK (for concomitant myositis), CK-MB. Repeat troponin, CK and EKG 2-3 days. If troponin and labs normalize may resume therapy. If labs worsen or symptoms develop then treat as below. Hold pending evaluation
Grade ≥2 with suspected myocarditis	Hold dose.** Admit to hospital. Cardiology consult. Rule out MI and other causes of cardiac disease. Cardiac Monitoring. Cardiac Echo. Consider cardiac MRI and cardiac biopsy. Initiate high dose methylprednisolone. If no improvement within 24 hours, add either infliximab, ATG or tacrolimus. Consult algorithm for more details. Resume therapy if there is a return to baseline and myocarditis is excluded or considered unlikely.
Grade ≥2 with confirmed myocarditis	Off protocol therapy. Admit to CCU (consider transfer to nearest Cardiac Transplant Unit). Treat as above. Consider high dose methylprednisolone Add ATG or tacrolimus if no improvement. Off treatment.

*Including CHF, LV systolic dysfunction, Myocarditis, CPK, and troponin
**Patients with evidence of myositis without myocarditis may be treated according as "other event"
Note: The optimal treatment regimen for immune mediated myocarditis has not been established.
Since this toxicity has caused patient deaths, an aggressive approach is recommended.

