6.2 Nivolumab

No dose reductions for Nivolumab are allowed. If Nivolumab is held on Day 1 of a new cycle, treatment with Lenalidomide/Dexamethasone will also be delayed. If Nivolumab is held during any cycle on day 15, the treating investigator should decide if lenalidomide and/or dexamethasone will be skipped using recommended guidance for retreatment below. Nivolumab may be delayed for up to 21 days or 3 weeks. A delay of up to 14 days will be allowed for participants for non-AE related events (i.e.; vacation, family emergency, etc) after discussion with the overall PI. If an alternate treatment plan for a suspected nivolumab related toxicity is proposed and is not listed in Table 11, you must first discuss and obtain approval from the Overall PI.

Dose delays and modifications will be made as indicated in the following table(s). The

CONFIDENTIAL

This document is confidential. Do not disclose or use except as authorized.

descriptions and grading scales found in the revised NCI Common Terminology Criteria for Adverse Events (CTCAE) version 4.03 will be utilized for dose delays and dose modifications. A copy of the CTCAE version 4.03 can be downloaded from the CTEP website

http://ctep.cancer.gov/protocolDevelopment/electronic_applications/ctc.htm.

* If any one of the study medications is permanently discontinued for any reason including toxicity, or FDA mandate, the patient may remain on the study at the discretion of the principal investigator.

Table 11 Suggested Guidelines for Nivolumab Suspected Toxicity

CTCAE 4.0 Category	CTCAE Grade	Nivolumab Action
Pneumonitis (See Section 6.2.1 for management guidelines)	Grade 1	Continue to treat- Do NOT OMIT
	Grade 2	Hold dose until resolved to \leq Grade 1
	\geq Grade 3	Permanently discontinue nivolumab
Colitis (See Section 6.2.2 for management guidelines)	Grade 1	Continue to treat- Do NOT OMIT
	Grade 2 or Grade 3	Hold dose until resolved to \leq Grade 1
	Grade 4	Permanently discontinue nivolumab
Increase in AST and/or ALT (See Section 6.2.3 for management guidelines)	Grade 1	Continue to treat- Do NOT OMIT
	Grade 2	Hold dose until resolved to \leq Grade 1
	\geq Grade 3	Permanently discontinue nivolumab
Increase in Blood Bilirubin (See Section 6.2.3 for management guidelines)	Grade 1	Continue to treat- Do NOT OMIT
	Grade 2	Hold dose until resolved to \leq Grade 1
	\geq Grade 3	Permanently discontinue nivolumab

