Increase in Creatinine (See Section 6.2.4 for management guidelines)	Grade 1	Continue to treat- Do NOT OMIT
	Grade 2 or Grade 3	Hold dose until resolved to \leq Grade 1
	Grade 4	Permanently discontinue nivolumab
All other related toxicities not listed previously in this table (See Section 6.2.6 for management guidelines)	Grade 1	Continue to treat- Do NOT OMIT
	Grade 2	Continue to treat- Do NOT OMIT
	Grade 3	Hold dose until resolved to \leq Grade 1
	Recurrent Grade 3 or	Permanently discontinue nivolumab

CONFIDENTIAL

This document is confidential. Do not disclose or use except as authorized.

	Grade 4	
--	---------	--

If the patient discontinues nivolumab, he or she does not need to come off protocol therapy

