6.2.2 Immune-mediated colitis

Monitor patients for immune-mediated colitis. Administer corticosteroids at a dose of 1 to 2 mg/kg/day prednisone equivalents followed by corticosteroid taper for severe (Grade 3) or life-threatening (Grade 4) colitis. Administer corticosteroids at a dose of 0.5 to 1 mg/kg/day prednisone equivalents followed by corticosteroid taper for moderate (Grade 2) colitis of more than 5 days duration; if worsening or no improvement occurs despite initiation of corticosteroids, increase dose to 1 to 2 mg/kg/day prednisone equivalents. Withhold NIVOLUMAB for Grade 2 or 3 immune-mediated colitis. Permanently discontinue NIVOLUMAB for Grade 4 colitis or for recurrent colitis upon restarting NIVOLUMAB

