7.2.1.2 Other Immune Mediated Adverse Events

For suspected immune-related adverse reactions, adequate evaluation should be performed to confirm etiology or exclude other causes. Based on the severity of the adverse reaction, nivolumab should be withheld or discontinued, and corticosteroids administered accordingly. Upon improvement, nivolumab may be resumed after corticosteroid taper. If there is recurrence of any Grade 3 or 4 immune-related adverse reactions or life-threatening immune-related adverse reactions, nivolumab must be permanently discontinued. Rare cases of myotoxicity (myositis, myocarditis, and rhabdomyolysis), some with fatal outcome, have been reported with nivolumab. If a patient develops signs and symptoms of myotoxicity, close monitoring should be implemented, and the patient referred to a specialist for assessment and treatment without delay. Based on the severity of myotoxicity, nivolumab should be withheld or discontinued, and appropriate treatment instituted. For Grade 3 myocarditis, nivolumab should be permanently discontinued.

The following events have been identified during post approval use of nivolumab. Because reports are voluntary from a population of unknown size, an estimate of frequency cannot be made.

- Solid organ and tissue transplant rejection has been reported in patients who have previously undergone transplantation and who were subsequently treated with programmed cell death 1/programmed cell death ligand 1 (PD-1/PD-L1) inhibitors, including nivolumab. Treatment with nivolumab may increase the risk of rejection in solid organ or tissue transplant recipients.
- Rapid-onset and severe GVHD, some with fatal outcome, has been reported in patients who had undergone prior allogeneic HSCT and subsequently received PD-1/PD-L1 inhibitors.

CONFIDENTIAL

This document is confidential. Do not disclose or use except as authorized.

Subjects should be screened to determine whether they have undergone a prior allogeneic HSCT prior to participating in nivolumab clinical trials.

- Complications of allogeneic HSCT after treatment with PD-1/PD-L1 inhibitors including nivolumab, administered before allogeneic HSCT, may be associated with an increased risk of transplant-related complications, including GVHD. Fatal cases have been reported in clinical studies. Patients should be monitored closely for early evidence of transplant-related complications

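### The nivolumab toxicity passages conflict on confirmed myocarditis, on recurrent colitis and on the length of a hold managed under 6.2.6, and need to be reconciled

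*Combined protocol and SAP*

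**What the plan says.** Section 6.2 allows no dose reduction of nivolumab and limits a hold: "Nivolumab may be delayed for up to 21 days or 3 weeks". Table 11, titled "Suggested Guidelines for Nivolumab Suspected Toxicity", gives an action by event and grade. It has rows for pneumonitis, colitis, transaminases, bilirubin and creatinine, but none for cardiac events. Its residual row is labelled "All other related toxicities not listed previously in this table (See Section 6.2.6 for management guidelines". That row continues treatment at Grades 1 and 2, holds at Grade 3, and stops nivolumab permanently at recurrent Grade 3 or at Grade 4. The note beneath the table reads "If the patient discontinues nivolumab, he or she does not need to come off protocol therapy".

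Other passages cover the same events:

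- **Cardiac.** Section 6.2.7 is a separate table whose action column is headed for nivolumab. At Grade 1 or below it says "Hold dose pending evaluation and observation". At Grade 2 or above it holds for suspected myocarditis and takes the patient off protocol therapy for confirmed myocarditis. Section 7.2.1.2 withholds or discontinues nivolumab according to the severity of myotoxicity and adds "For Grade 3 myocarditis, nivolumab should be permanently discontinued".
- **Colitis.** Section 6.2.2 says "Permanently discontinue NIVOLUMAB for Grade 4 colitis or for recurrent colitis upon restarting NIVOLUMAB". Section 7.2.1.2 requires a permanent stop when an immune-related reaction recurs at Grade 3 or 4 or is life-threatening.
- **Length of hold.** Once the reaction improves to Grade 1 or less, 6.2.6 says to "initiate corticosteroid taper and continue to taper over at least 1 month", and restart is considered after the taper is complete. Section 6.1 makes three weeks the maximum toxicity delay before permanent discontinuation. It lets the Principal Investigator approve a longer delay for a patient who is benefiting.

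Sections 6.1 and 6.2 also leave it to the Principal Investigator whether a patient who permanently stops one drug stays on study. Sections 1.1 and 5.1 record that since September 2017 all patients are to discontinue nivolumab. They may continue lenalidomide, with or without dexamethasone.

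**The concern.** A site handling one of these events can find different instructions depending on which section it opens. The cardiac case matters most. Section 6.2.7 itself notes that this toxicity has caused deaths, and 6.2.6 warns that immune reactions can appear after nivolumab is stopped. The hold on nivolumab therefore does not close the question. A patient still on lenalidomide may develop myocarditis late, and the text does not settle whether the remaining drugs stop as well.

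The conflicts also affect how past holds and removals are classified, because 5.5 requires the reason and date of removal from protocol therapy to be recorded.

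**Working it through.** No sample-size or error-rate figure is involved. The check sets the passages side by side by event and grade, followed by one day count.

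**1. Cardiac events**

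| Event and grade | Table 11 read alone (residual row) | 6.2.7 | 7.2.1.2 |
|---|---|---|---|
| Cardiac, Grade 1 | continue | hold | by severity, if myotoxicity |
| Confirmed myocarditis, Grade 2 | continue | off protocol therapy | withhold or discontinue nivolumab by severity |
| Confirmed myocarditis, first Grade 3 | hold | off protocol therapy | permanently stop nivolumab |

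The last two columns conflict in scope without any help from the residual row. Section 6.2.7 removes the patient from protocol therapy, under a heading about nivolumab. Section 7.2.1.2 addresses nivolumab only. The note under Table 11 says stopping nivolumab does not oblige the patient to leave protocol therapy, and 6.1 and 6.2 leave staying on study to discretion. The first column adds a cross-reference fault: the residual row cites 6.2.6 and not 6.2.7.

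**2. Recurrent colitis after restart** (grade taken as that of the recurrence)

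| Grade | Table 11 | 6.2.2 | 7.2.1.2 |
|---|---|---|---|
| 1 | continue | permanently stop | stop not required |
| 2 | hold until Grade 1 or less | permanently stop | stop not required |
| 3 | hold until Grade 1 or less | permanently stop | permanently stop |
| 4 | permanently stop | permanently stop | permanently stop |

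The passages agree only at Grade 4. Table 11 has no recurrence rule for colitis, although its colitis row refers to 6.2.2 for management.

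**3. Length of hold, reactions managed under 6.2.6 only**

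- Limit in 6.2: 21 days.
- Minimum taper in 6.2.6: one month, taken as 28 to 31 days.
- Overrun = taper − limit: 28 − 21 = 7 days; 31 − 21 = 10 days.

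Time to reach Grade 1 or less comes before the taper and adds to this. The count assumes that the hold begins no later than the taper. Section 6.2 does not say where the delay starts. Suppose it starts at the first missed dose and the taper began just after the previous dose. With dosing on Days 1 and 15, up to 14 days of taper could then pass before a dose is due. That leaves 28 − 14 = 14 to 31 − 14 = 17 days, inside the limit. On the ordinary count from the start of the taper, restart after a full taper is possible only through the exception in 6.1.

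**The case against.** The strongest reply is that the specific rule governs the general one. Section 6.2.7 is a dedicated cardiac table. Its footnote sends only myositis without myocarditis to the other-event route, and footnote 15 of the study calendar directs cardiac concerns to 6.2.7. Table 11 is only a set of suggestions. On this view a reader might infer from the residual row that sites are told to keep dosing through confirmed myocarditis, but the documents do not support that as the intended rule. This part stands: the instruction to continue arises only when Table 11 is read alone, and it is mainly a missing cross-reference.

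Two similar replies succeed in part. Leaving protocol therapy also satisfies an instruction to stop nivolumab, and the Table 11 note is a permission that 6.2.7 could override. No passage says that it does, however, and the 6.2.7 column heading points to nivolumab alone. For colitis, 6.2.2 can be read as supplying the recurrence rule that Table 11 omits. The difference from 7.2.1.2 at the lower grades is then one of a stricter specific rule, but a site using the table alone would still hold.

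A reader might also infer that every steroid-treated reaction breaches the 21-day limit. That is too strong. Only 6.2.6 gives a taper length; 6.2.1, 6.2.2 and 6.2.4 mention a taper without a duration, and 6.2.3 mentions none. Section 6.1 also offers an exception.

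Finally, nivolumab is already stopped, and 5.5 removes patients for unacceptable adverse events. Both are true, and they reduce the practical reach. Section 5.5 does not say whether a given late myocarditis counts as unacceptable, so the question about the remaining drugs stays open.

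**Conclusion.** The conflicts are real and stand in the current text, but they are narrower than the side-by-side tables first suggest.

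- **Cardiac:** the firm conflict is one of scope. For confirmed myocarditis at Grade 2 or above, 6.2.7 ends protocol therapy, while 7.2.1.2 and the Table 11 note deal with nivolumab alone.
- **Colitis:** instructions for a recurrence differ at Grades 1 to 3, softened by Table 11's reference to 6.2.2.
- **Hold length:** the overrun is at least 7 to 10 days for reactions under 6.2.6, assuming a month of 28 to 31 days and a delay counted from the start of the taper or earlier.

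Two stronger readings are not supported. One is that a single event and grade carries four separate instructions. At most three passages instruct on any one case, and for confirmed myocarditis one of these applies only if 6.2.7 is overlooked. The other is that the conflict distorts the 2-year endpoint. Section 13.1.1 includes everyone who received one dose, 5.6 continues follow-up for three years after removal from therapy, and 5.7 does not list leaving therapy as a reason to leave the study.

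With nivolumab stopped, the live consequence is whether a late myocarditis ends lenalidomide and dexamethasone, together with the classification of past holds and removals. The point should be addressed because the event can be fatal and the correction is cheap.

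**What to change.** Reconcile 6.1, 6.2, Table 11 and its note, 6.2.2, 6.2.6, 6.2.7 and 7.2.1.2 so that each event and grade carries one instruction. In particular:

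- add cross-references in both directions between Table 11 and 6.2.7;
- wherever a patient is taken off, state whether this means nivolumab or all protocol therapy;
- give one rule for recurrent colitis in all three places;
- state whether the exception in 6.1 applies to the limit in 6.2, and from which day the delay is counted.

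Which rule stands in each case is for the clinical team to decide; this review does not choose. The cost is a text amendment and a site memo, with no new procedures.

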6.3 Lenalidomide

Hematologic Toxicities: For adverse hematologic events that are considered possibly, probably or definitely related to Lenalidomide, the following criteria for retreatment and dose modification should be followed unless discussed and approved first by the overall principal

CONFIDENTIAL

This document is confidential. Do not disclose or use except as authorized.

investigator. The treating investigator should determine the clinical significance of laboratory values and attribution to study medications before a treatment decision is made. All instances where lenalidomide is held, the dose will be considered missed, and will not be made up.

Non Hematologic Toxicity: For adverse non hematologic events that are considered to be possibly, probably or definitely related to Lenalidomide, the following criteria for retreatment and dose modification should be followed unless discussed and approved first by the overall principal investigator. The treating investigator should determine the clinical significance of laboratory values or radiographic findings and attribution to study medications before a treatment decision is made. All instances where lenalidomide is held, the dose will be considered missed, and will not be made up.

Dose delays and modifications should be made as indicated in the following table(s) unless first discussed with the Overall PI. The descriptions and grading scales found in the revised NCI Common Terminology Criteria for Adverse Events (CTCAE) version 4.0 will be utilized for dose delays and dose modifications. A copy of the CTCAE version 4.0 can be downloaded from the CTEP website

http://ctep.cancer.gov/protocolDevelopment/electronic_applications/ctc.htm.

Table 12 Lenalidomide Hematologic Toxicities

CTCAE 4.0 Category	CTCAE Grade	Lenalidomide Dose Modification
Absolute Neutrophil Count (ANC)¹	Grade 1 or Grade 2	Continue to treat- Do NOT OMIT and DO NOT REDUCE therapy
	Grade 3	Hold dose Administer Filgrastim Resume at same dose when ANC is \geq 1000 if neutropenia is the only hematologic toxicity If other hematologic toxicity \geq Grade 2 is present, reduce dose one level when ANC \geq 1000
	Grade 4	Hold dose Administer Filgrastim Resume therapy at one dose level lower when ANC is \geq 1000
Neutropenia with Fever ANC <1000 and temperature \geq 38.5° C or 101°F	Grade 3 or Grade 4	Hold dose Administer Filgrastim Reduce dose one level when ANC \geq 1000
Thrombocytopenia	Grade 1 or Grade 2	Continue to treat- Do NOT OMIT and DO NOT REDUCE therapy

CONFIDENTIAL

This document is confidential. Do not disclose or use except as authorized.

Aspirin prophylaxis should be held if platelets are $\leq 50,000$	Grade 3 or Grade 4	
Provide platelet transfusion support Redraw platelets
 
If redrawn platelet value $\geq 50,000$ -> Do NOT OMIT and DO NOT REDUCE therapy
 
If redrawn platelet value $< 50,000$ continue to transfuse at the discretion of the investigator and hold therapy until platelets are $\geq 50,000$ on Day 1 or $\geq 30,000$ intracycle
 
Resume therapy at one dose level lower when the patient's platelets are $\geq 50,000$ on Day 1 or $\geq 30,000$ intracycle

	Grade 1 Grade 2 Grade 3	
Continue to treat- Do NOT OMIT and DO NOT REDUCE therapy Transfuse at the discretion of treating investigator

Anemia	Grade 4	
Hold treatment Transfuse Resume treatment when hemoglobin ≥ 8.0 g/dL DO NOT REDUCE therapy

¹ ANC can be calculated two ways: From the percentage of neutrophils: White Blood Count (WBC) x total neutrophils (polys% + bands%) x 10. From the absolute number of cells: (Absolute polys + Absolute bands) x 10.

Table 13 Lenalidomide Non Hematologic Toxicities

CTCAE 4.0 Category	CTCAE Grade	Lenalidomide Dose Modification
Infection or Viral Illness with ANC¹ ≥ 1000 Including herpes zoster reactivation	N/A	
Day 1 of Cycle: Delay cycle until infection/viral illness has resolved. Resume treatment at the same dose level. Do not dose reduce.
 
Intracycle: Hold lenalidomide for a maximum of 21 days to allow for recovery. Resume treatment at same dose level.
 
If patient has delay of greater than 21 days, the patient must come off-study

CONFIDENTIAL

This document is confidential. Do not disclose or use except as authorized.

Infection or Viral Illness with ANC¹ < 1000	N/A	
Day 1 of Cycle: Delay cycle until infection/viral illness has resolved. Administer filgrastim or equivalent as indicated.
 
Reduce one dose level when infection/virus has resolved, and ANC \geq1000
 
Intracycle: Hold lenalidomide for a maximum of 21 days. Reduce one dose level when infection/virus has resolved and ANC \geq 500
 
If patient has a delay of less than or equal to 21 days, dose reduce to next dose level. If patient has delay of greater than 21 days, the patient must come off-study

--	------------	---

Allergic reaction or hypersensitivity to Lenalidomide Including Rash related to Lenalidomide	Grade 1 Grade 2 Grade 3 or Grade 4	
Continue to treat- Do NOT OMIT and DO NOT REDUCE therapy
 
Continue to treat- Do NOT OMIT and DO NOT REDUCE therapy
 
Hold lenalidomide Follow at least weekly. If toxicity resolves to \leq grade 2, restart at next lower dose level

Renal/Metabolic For all grades, provide hydration and other supportive care as needed at the discretion of the treating investigator	Grade 1 Grade 2 Grade 3 or Grade 4	
Continue to treat- Do NOT OMIT and DO NOT REDUCE therapy
 
Hold Lenalidomide until < grade 2 and resume treatment at the same dose level If toxicity recurs, dose reduce one dose level at the treating investigator's discretion
 
Hold Lenalidomide until < grade 2 and resume treatment with one dose level reduction If the toxicity remains \geq grade 3, omit dose and restart at subsequent scheduled visit with one dose level

CONFIDENTIAL

This document is confidential. Do not disclose or use except as authorized.

		reduction If treatment-related toxicity occurs on day one of the cycle, the cycle will be delayed.
--	--	---

Diarrhea, Constipation, Nausea, or Vomiting	Grade 1	Continue to treat- Do NOT OMIT and DO NOT REDUCE therapy
	Grade 2	Treat at the discretion of the investigator Provide aggressive supportive care DO NOT REDUCE therapy
	Grade 3	Hold Lenalidomide until toxicity resolves to < grade 2 If the patient has received maximum supportive care, resume therapy with one dose level reduction
	Grade 4	Hold Lenalidomide until toxicity resolves to < grade 2 Resume therapy with one dose level reduction
All other related toxicities not listed previously in this table	Grade 1	Continue to treat- Do NOT OMIT and DO NOT REDUCE therapy
	Grade 2	Continue to treat- Do NOT OMIT and DO NOT REDUCE therapy unless considered to be a clinically significant finding Provide supportive care as needed

CONFIDENTIAL

This document is confidential. Do not disclose or use except as authorized.

	Grade 3	Hold Lenalidomide until toxicity resolves to < grade 2 Resume therapy with one dose level reduction at the discretion of the treating investigator
	Grade 4	Hold Lenalidomide until toxicity resolves to < grade 2 Resume therapy with one dose level reduction If treatment-related toxicity occurs on day one of the cycle, the cycle will be delayed. If patient has a delay of less than or equal to 21 days, dose reduce to next dose level. If patient has delay of greater than 21 days, the patient must come off-study

If the patient discontinues lenalidomide, he or she does is not required to come off protocol therapy.

Table 14 Lenalidomide Dose Reduction

Dose Level	Lenalidomide Dose
0	25 mg
-1	20 mg
-2	15 mg
-3	10 mg
-4	5 mg

If lenalidomide is reduced for any toxicity, the dose may not be re-escalated.

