3.1.3 ECOG Performance Status (PS) 0, 1, or 2 (Appendix A)

3.1.4 The following laboratory values obtained ≤ 21 days prior to registration and confirmed prior to the first dose of study drug:

- ANC $\geq 1000/\mu\text{L}$
- PLT $\geq 50,000/\mu\text{L}$. Platelet transfusions to help patients meet eligibility criteria are not allowed within 3 days before study enrollment.
- Total bilirubin ≤ 1.5 mg/dL (If total is elevated check direct and if normal patient is eligible.)
- AST $\leq 3 \times$ institutional upper limit of normal (ULN)
- ALT $\leq 3 \times$ institutional upper limit of normal (ULN)
- WBC $\geq 2000/\mu\text{L}$

3.1.5 Ability to understand and willingness to sign a written informed consent before performance of any study-related procedure not part of normal medical care, with the understanding that consent may be withdrawn by the subject at any time without prejudice to future medical care.

CONFIDENTIAL

This document is confidential. Do not disclose or use except as authorized.

3.1.6 Female patients who are postmenopausal for at least 1 year before the screening visit or are surgically sterile. Females of childbearing potential* must have a negative serum or urine pregnancy test with a sensitivity of at least 25 mIU/mL within 10 – 14 days and again within 24 hours prior to prescribing lenalidomide for Cycle 1 (prescriptions must be filled within 7 days as required by Revlimid REMS®) and must either commit to continued abstinence from heterosexual intercourse or begin TWO acceptable methods of birth control, one highly effective method and one additional effective method AT THE SAME TIME, at least 28 days before she starts taking lenalidomide. Females of reproductive potential must agree to follow instructions for method(s) of contraception for the duration of treatment with any study drug(s) plus 5 half-lives of study plus 30 days (duration of ovulatory cycle) for a total of 120 days after their last dose of lenalidomide (Revlimid). Women must not breastfeed.

Female patients who are of childbearing potential must use contraception for 5 half-lives plus 30 days after their last dose of nivolumab for a total of 5 months.

* *A female of childbearing potential is a sexually mature female who:*

- *Has not undergone a hysterectomy (the surgical removal of the uterus) or bilateral oophorectomy (the surgical removal of both ovaries) or*

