5.3 General Concomitant Medication and Supportive Care Guidelines

5.3.1 Medications and supportive care

- Patients who experience worsening neuropathy from baseline should be observed for recovery, have dose reductions/delays as indicated in the protocol, and any supportive therapy or intervention may be initiated as appropriate at the discretion of the investigator.
- Supportive measures consistent with optimal patient care may be given throughout the study.
- Stem cell collection may be performed at the time of best response (PR, VGPR or CR or at the investigator's discretion) or after 6 cycles of therapy for those who are transplant eligible, and/or who plan to pursue transplant in the future. The standard mobilization procedures of the treating institution should be followed. Plerixafor should be the preferred mobilization agent, though cyclophosphamide or other agent may be used at the investigator's discretion. A delay of no more than 3 weeks is allowed between the end of collection and re-initiation of therapy especially if chemotherapy such as high dose cyclophosphamide was used for stem cell mobilization. Mobilization should occur as soon as possible after study treatment is stopped.
- Use of white cell growth factors (Filgrastim or acceptable equivalent) is allowed for management of treatment-induced neutropenia at physician discretion. Filgrastim or equivalent should be given according to local institutional guidelines or per the package insert. Pegfilgrastim is not to be used in place of filgrastim.
- Patients may be transfused with red cells and platelets as clinically indicated and according to institutional guidelines.
- Patients may receive bisphosphonates per recommendations of myeloma therapy, or may follow local standard of care. A note should be placed about patients who are not receiving bisphosphonates, such as osteonecrosis of the jaw.
- If nausea and/or vomiting is/are noted at any point in time, premedication with prochlorperazine or other antiemetics may be used before future doses. Antiemetics, including 5-HT3 serotonin receptor antagonists, may be used as needed at the discretion of the investigator.

CONFIDENTIAL

This document is confidential. Do not disclose or use except as authorized.

- If nausea persists in spite of the use of standard antiemetics, additional symptom management should be initiated per institutional standard.

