5.4.2 Thrombocytopenia

- Blood counts will be monitored regularly as outlined in the protocol with additional testing obtained according to standard clinical practice. Thrombocytopenia may be severe but has been manageable with platelet transfusions according to standard clinical practice. Lenalidomide administration should be modified as noted as per dose modification recommendations in the protocol when thrombocytopenia occurs (see Section 6.3). Therapy may be reinitiated at a reduced level upon recovery of platelet counts.
- A rare risk is thrombotic thrombocytopenic purpura (TTP), a rare blood disorder where blood clots form in small blood vessels throughout the body characterized by thrombocytopenia, petechiae, fever, or possibly more serious signs and symptoms. TTP should be managed symptomatically according to standard medical practice.

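### Table 12 sets the lenalidomide dose in Grade 3-4 thrombocytopenia from a platelet count redrawn after transfusion, and it disagrees with section 6.1 and with the Day 15 nursing criterion

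*Combined protocol and SAP*

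**What the plan says.** Table 12 (section 6.3) has one row for Grade 3 or Grade 4 thrombocytopenia. It starts with "Provide platelet transfusion support Redraw platelets" and then splits on the redrawn value:

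- At or above 50,000: "If redrawn platelet value $\geq 50,000$ -> Do NOT OMIT and DO NOT REDUCE therapy".
- Below 50,000: "continue to transfuse at the discretion of the investigator and hold therapy until platelets are" at least 50,000 on Day 1 or at least 30,000 intracycle. Then "Resume therapy at one dose level lower when the patient's platelets are" at those same levels.

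The note under Table 14 says that a lenalidomide dose reduced for toxicity is not raised again.

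Two other places govern the same decision:

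- Section 6.1 requires at least 50,000 platelets to start a new lenalidomide cycle. If this is not met on Day 1, all drugs are delayed for 1 week and the patient is then re-evaluated.
- The special nursing considerations sheet at the end of the document gives Day 15 criteria. For lenalidomide its platelet line is 30 or more, with no dose change mentioned.

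Section 6.3 also has a general clause: "The treating investigator should determine the clinical significance of laboratory values and attribution to study medications before a treatment decision is made". It allows departures that the overall principal investigator has approved first.

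**The concern.** A dose-modification rule should respond to what the drug has done to the patient. Here the deciding count is taken after the treatment that raises it, and the time between the two is left open. Two patients with the same lenalidomide-related nadir can therefore receive opposite default instructions, depending on how well they respond to the transfusion and how soon the blood is redrawn.

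Sites also find different answers in different places. On Day 1, section 6.1 and Table 12 disagree. During a cycle, Table 12 is hard to apply as printed and does not match the nursing sheet.

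The rule is still in use. Sections 1.1 and 5.1 record that nivolumab was stopped and accrual closed in September 2017, but participants may elect to stay on lenalidomide, with or without dexamethasone.

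**Working it through.** The plan states no figure on this point to reproduce, so the check sets the passages side by side.

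**Step 1. Order of events.** Table 12 lists transfusion, then redraw. In the branch below 50,000 the site is told to *continue* transfusing, which confirms that the redraw follows a transfusion. The row gives no interval and asks for no untransfused count.

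**Step 2. What selects the branch.** Let X be the patient's own count and T the rise from transfusion at the time of the redraw. The redrawn value is X + T, so dosing continues unchanged when T ≥ 50,000 − X. With illustrative values of X (assumed, not from the documents):

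| Own count X | Rise needed for unchanged dosing |
|---|---|
| 45,000 | 50,000 − 45,000 = 5,000 |
| 30,000 | 50,000 − 30,000 = 20,000 |
| 20,000 | 50,000 − 20,000 = 30,000 |

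For a fixed X, the branch depends only on T, that is, on transfusion response and redraw timing. This takes Grade 3-4 to mean a count below 50,000. The grade cut-offs are not printed in the document, but that reading fits Table 12's own threshold.

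**Step 3. Day 1, first count 40,000 (assumed).**

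| Source | Instruction |
|---|---|
| Section 6.1 | Below 50,000: delay all drugs 1 week, then re-evaluate |
| Table 12, redraw ≥ 50,000 (rise ≥ 10,000) | Lenalidomide neither omitted nor reduced |
| Table 12, redraw < 50,000 | Hold until ≥ 50,000, resume one level lower |

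Section 6.1 does not say whether a transfused recheck on the same day would satisfy its criterion.

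**Step 4. Day 15, first count 40,000 (assumed).**

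| Source | Instruction |
|---|---|
| Nursing sheet | 40 ≥ 30: platelet criterion for lenalidomide met |
| Table 12, redraw ≥ 50,000 | Lenalidomide neither omitted nor reduced |
| Table 12, redraw 30,000-49,999 | Hold until ≥ 30,000, then resume one level lower |

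In the last line the release condition is met when the hold begins, so the hold has no length, yet the dose still falls one level. The nursing sheet prints no unit. Its Day 1 line of 50 matches the 50,000 in section 6.1, so 30 is read as 30,000.

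**Step 5. Size of the dose consequence.** Table 14 steps are 25, 20, 15, 10 and 5 mg. One level is 5 mg: 5/25 = 20%, 5/20 = 25%, 5/15 = 33% or 5/10 = 50% of the current dose. Maintenance starts at 15 mg or lower (Table 8), so a single step there is at least a third. In induction, one step from 25 to 20 mg does not carry into maintenance, because only reductions below 15 mg do.

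**The case against.** The strongest reply is that section 6.3 is not mechanical: the investigator judges clinical significance and attribution before any treatment decision, and the overall principal investigator may approve departures. That softens the rule. It does not change the default, since the clause does not mention transfusion or say which count to use.

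A second reply is that the redraw was meant only to confirm the low value. The printed order does not say so; if that was the intent, the row still needs rewording.

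Several stronger inferences are tempting, and the documents do not support them:

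- *Contradiction with section 3.1.4.* That section says "Platelet transfusions to help patients meet eligibility criteria are not allowed within 3 days before study enrollment". It is an entry rule counted from enrollment and does not govern dosing on treatment.
- *Contradiction with section 5.4.2.* Its sentence "Therapy may be reinitiated at a reduced level upon recovery of platelet counts" is permissive, and the sentence before it defers to section 6.3.
- *Contradiction with section 5.3.1.* "Patients may be transfused with red cells and platelets as clinically indicated and according to institutional guidelines" is general supportive-care text beside a specific table row.
- *Distorted toxicity summaries.* The row is entered only after a Grade 3 or 4 count has been recorded. Section 7.1.1 makes a laboratory value an adverse event when it leads to therapeutic intervention, and section 7.9 requires all adverse events to be reported. A higher count after transfusion does not erase the event, so section 13.1.2 needs no change.

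It also stands that reach is limited: accrual is closed, and only participants who elect to stay on lenalidomide are exposed to the rule.

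**Conclusion.** The point holds in a bounded form. Table 12 bases the lenalidomide decision on a count confounded by transfusion and of undefined timing. It conflicts with section 6.1 on Day 1. During a cycle, for redrawn counts of 30,000 to 49,999, it is inconsistent with itself and does not match the nursing sheet.

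The consequence per event is the difference between an unchanged current dose level and a hold with a 5 mg step down that may not be reversed. A reader might infer that the redrawn count measures only donor platelets, or that patients continue at full dose. Neither follows: the count is the patient's own plus donor platelets, and the current level may already be below 25 mg.

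No share of events or patients can be given. The documents state neither how often Grade 3-4 thrombocytopenia occurs in this trial nor how much a transfusion raises the count, and any percentage would only restate assumed inputs. The conclusion assumes that Grade 3-4 means a count below 50,000 and that the nursing sheet's figures are in thousands.

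**What to change.** The sponsor's clinical leads should reconcile the thrombocytopenia row of Table 12, the Day 1 criterion and delay rule in section 6.1, and the Day 15 platelet criterion on the nursing considerations sheet. Each place should state which platelet count governs the lenalidomide decision, on Day 1 and intracycle, and how that count is timed relative to any transfusion. The intracycle instruction for redrawn counts of 30,000 to 49,999 should be made consistent within Table 12. No threshold, dose or clinical rule is proposed here.

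The cost is a wording amendment in three places. The downside is small: depending on the count chosen, some patients may have more lenalidomide doses held.
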